## Non-interventional study

### Protocol originator:-

[REDACTED]

[REDACTED] India

This ~~confidential~~ document is the property of Novo Nordisk. ~~No unpublished information contained herein may be disclosed without prior written approval from Novo Nordisk. Access to this document must be restricted to relevant parties.~~

Title	A multi-centre, prospective, open-label, single-arm, non-interventional post marketing surveillance (PMS) study of Tresiba ® (insulin degludec) to evaluate long term safety and efficacy in patients with diabetes mellitus in routine clinical practice in India.
Protocol version identifier	1.0
Date of last version of protocol	25 July 2013
EU PAS Register number	Study not registered
Active substance	Insulin degludec
Medicinal product	Tresiba ®
Product reference	Not Applicable
Procedure number	Not Applicable
Marketing authorisation holder(s)	Novo Nordisk India Pvt Ltd
Joint Post Authorisation Safety Study (PASS)	Yes
Research question and objectives	To assess the safety of long-term treatment with insulin degludec (Tresiba ® ) in insulin requiring patients with diabetes mellitus, initiating treatment with Tresiba ® under routine clinical practice in India.
Country(-ies) of study	India
Author	██████████, ██████ Novo Nordisk India Pvt Ltd

## 1 List of abbreviations

ADR	Adverse Drug Reaction
AE	Adverse Event
BMI	Body Mass Index
CRF	Case Report Form
CRO	Contract Research Organisation
CV	Curriculum Vitae
DCF	Data Clarification Form
EAS	Efficacy Analysis Set
EDC	Electronic Data Capture
ENCePP	European Network of Centres for Pharmacoepidemiology and Pharmacovigilance
FAS	Full Analysis Set
FBG	Fasting Blood Glucose
FPG	Fasting Plasma Glucose
GVP	Good Pharmacovigilance Practice
GPP	Good Pharmacoepidemiology Practice
HbA1c	Glycated Haemoglobin
ICF	Informed consent form
IEC	Independent Ethics Committee
IRB	Institutional Review Board
LAR	Legally Acceptable Representative
OAD	Oral anti-diabetic drugs
PASS	Post Authorisation Safety Study
PMS	Post Marketing Surveillance
PI	Package Insert
PPBG	Postprandial Blood Glucose
PPPG	Postprandial Plasma Glucose
PRAC	Pharmacovigilance Risk Assessment Committee
SAE	Serious Adverse Event

SADR	Serious Adverse Drug Reaction
SOC	System Organ Class
TC	Technical Complaint
T1DM	Type 1 Diabetes mellitus
T2DM	Type 2 Diabetes mellitus
UTN	Universal Trial Number
WHO	World Health Organization

## **2 Responsible parties**

Novo Nordisk will be responsible for the preparation of the protocol. Data management will be delegated under an agreement of transfer of responsibilities to an external CRO. Statistics and the study report will be performed by Novo Nordisk or delegated under an agreement of transfer of responsibilities to an external CRO. All Novo Nordisk procedures and policies will be met by the CRO.

The physician is accountable for the conduct of the study. If any tasks are delegated, the physician should maintain a list of appropriately qualified persons to whom he/she has delegated specified significant study-related duties. The medical care given to, and medical decisions made on behalf of patients should always be the responsibility of a qualified physician

The physician must follow the instructions from Novo Nordisk when processing data. The physician must take all necessary technical and organisational safety measures to prevent accidental or wrongful destruction, loss or deterioration of data. The physician must prevent any unauthorised access to data or any other processing of data against applicable law. Upon request from Novo Nordisk, the physician must provide Novo Nordisk with the necessary information to enable Novo Nordisk to ensure that such technical and organisational safety measures have been taken.

## **3 Abstract**

### **3.1 Title**

A multi-centre, prospective, open-label, single-arm, non-interventional, post marketing surveillance (PMS) study of Tresiba® (insulin degludec) to evaluate long term safety and efficacy in patients with diabetes mellitus in routine clinical practice in India.

### **3.2 Rationale and background**

The rationale for conduct of this study in India is that it is a primary regulatory requirement by the Indian health authority to assess the safety of all medicinal products approved for clinical use

### **3.3 Research question and objectives**

The purpose of this post marketing surveillance (PMS) study (also called post authorization safety study (PASS) study) is to assess long-term safety and efficacy of Tresiba® in patients with diabetes mellitus requiring insulin therapy under normal clinical practice conditions

### **3.4 Study design**

This is a multi-centre, prospective, single-arm, open-label, non-interventional, post marketing surveillance (PMS) study (post authorization safety study (PASS) study) to evaluate safety and efficacy during long-term treatment with Tresiba® in patients with diabetes mellitus requiring insulin therapy under normal clinical practice conditions in India. Patients who qualify for starting treatment with Tresiba® based on the clinical judgment by their treating physician will be treated with Tresiba® according to routine clinical practice at the discretion of the treating physician. The assignment of the patient to Tresiba® is decided in advance of this protocol. The patients will be decided to be prescribed with Tresiba® by physicians before the enrolment in the study based on requirement and clinical judgement in diabetes management.

### **3.5 Population**

Patients with diabetes mellitus requiring insulin therapy who qualify for starting treatment with Tresiba® based on the clinical judgment by their treating physician during enrolment period. Patients are excluded if they have known or suspected allergy to Tresiba® or any of the excipients or in case of previous participation in this study. Patients can be withdrawn at their will at any time. Also, a patient may be withdrawn from this PMS/PASS at the discretion of the physician due to a safety concern.

### **3.6 Variables**

AEs/SAEs/ADRs/SADRs will be collected for safety evaluation and HbA1c, FPG and confirmed hypoglycaemic events will be evaluated for efficacy aspect of Tresiba®

### **3.7 Data sources**

The PMS/PASS study is conducted in a real-life setting and without extensive monitoring of the data collected. Only data obtained under normal clinical practice (i.e. available in patient's medical record or recall) will be recorded. Patients will not undergo any additional testing for the purposes of this PMS/PASS study. Hence there is a risk that complete data stated in the protocol are not always collected from all patients, though relevant measures will be employed to secure that all relevant data are reported and collected

### 3.8 Study size

The number of patients to be included in this study is 1000

### 3.9 Study duration

1 year

### 3.10 Data analysis

Safety and efficacy will be evaluated using descriptive statistics.

### 3.11 Milestones

FPFV will be attained by 31 Jan 2014 with LPLV by 31 Jan 2016 and study report by 30 May 2016

## 4 Amendments and updates

Amendment or update no	Date	Section of study protocol	Amendment or update	Reason

## 5 Milestones

Milestone	Planned date
Start of data collection	31 Jan 2014
End of data collection	31 Jan- 2016
End (or completion) of study	31 Jan 2016
Final report of study results	30 May 2016

The study has to be registered with CTRI (Clinical Trial Registry India) before the enrolment of first patient in the study in the following site [www.ctri.nic.in](http://www.ctri.nic.in) as per regulations of health authority of India.

## **6 Rationale and background**

The rationale for conduct of this study in India is that it is a primary regulatory requirement by the Indian health authority to assess the safety of all medicinal products approved for clinical use. In addition, although marketing approval for Tresiba® has been granted in India, there is a continuous need to monitor the safety of medicinal products as post-approval surveillance while they are used under normal clinical practice. Spontaneous reporting helps detect signals of safety concern and is a part of continuous safety surveillance. However, more formal studies or surveys constitute a proactive approach to planned collection of safety information and will in some instances identify unexpected ADRs.

## **7 Research question and objectives**

The purpose of this PMS/post authorization safety study (PASS) study is to assess long-term (1 year) safety and efficacy of Tresiba® in patients with diabetes mellitus requiring insulin therapy under normal clinical practice conditions

### **7.1 Primary objective**

To assess the safety of long-term treatment with insulin degludec (Tresiba®) in insulin requiring patients with diabetes mellitus, initiating treatment with Tresiba® under routine clinical practice in India.

### **7.2 Secondary objective(s)**

To assess safety and efficacy of long term (1 year) treatment with Tresiba®

### **7.3 Endpoints**

Primary endpoint

- Incidence of AEs by preferred term during 1 year of treatment

Secondary safety endpoint

- Incidence of the following events during 1 year of treatment:
  - SAEs by preferred term
  - SADRs by preferred term
  - ADRs by preferred term
  - Severe hypoglycaemia

## Secondary efficacy endpoints

- Change from baseline in HbA1c after 1 year of treatment
- Change from baseline in FPG after 1 year of treatment
- Incidence of confirmed hypoglycaemia during 1 year of treatment

## 8 Research methods

In this document physician refers to the individual overall responsible for the conduct of the non-interventional study at a study site.

### 8.1 Study design

#### 8.1.1 Type of study

This is a multi-centre, prospective, single-arm, open-label, non-interventional, post marketing study(PMS)/post authorization safety study (PASS) study to evaluate safety and efficacy during long-term treatment (1 year) with Tresiba® in patients with diabetes mellitus requiring insulin therapy under normal clinical practice conditions in India. A total of 1000 patients will be enrolled to investigate safety of Tresiba® of which approximately 10 patients per site will be selected by 100 physicians (both primary and secondary care physicians). Data will be collected at baseline (Visit 1), 3 months (Visit 2), 6 months (Visit 3) and finally at one year (Visit 4).

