### **8.2 Setting**

#### **8.2.1 Number of patients to be studied**

Planned number of patients to be included: 1000

Planned number of patients to complete the study: 800

Anticipated number of patients to be included in each country: India only-1000

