### **8.2.5 Rationale for selection criteria**

The assignment of the patient to Tresiba® is decided in advance of this the protocol and as part of current practice. Hence, the prescription of Tresiba is clearly separated from the decision to include the patient in the study.

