## **8.5 Study size**

The sample size calculation is based on the primary objective to evaluate the safety and tolerability of Tresiba®. A sample size of 1000 patients, assuming 20% dropouts who have been exposed to insulin degludec during the treatment will provide a probability of 80% of detecting at least one event that occurs with an incidence of 2 in 1000 patients or approximately 6 events with an incidence of 1/100 patients.

For an unobserved event, with the above sample size the upper limit of the 95% CI of the rate would be 0.375 per year. In other words for an unobserved event, a rate of 0.375 per year or larger can be excluded with 95% probability.

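### Section 8.1.1 has each physician select about 10 Tresiba starters with no enrolment order, so the single-arm AE incidence may not describe routine users

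*Protocol*

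**What the plan says.** Section 8.1.1 sets the size and its spread over sites. "A total of 1000 patients will be enrolled to investigate safety" of Tresiba, and "approximately 10 patients per site will be selected by 100 physicians (both primary and secondary care physicians". No rule for that selection follows.

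Sections 8.1.3, 8.2.5 and 8.2.6 make entry to the study a decision of its own, apart from prescribing. Section 8.2.5 puts it this way: "Hence, the prescription of Tresiba is clearly separated from the decision to include the patient in the study".

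The nearest text to an enrolment rule is in section 8.4.1: a patient who satisfies every inclusion criterion and no exclusion criterion is to be enrolled and given a number. It gives no order of approach.

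The primary endpoint in section 7.3 is "Incidence of AEs by preferred term during 1 year of treatment". Section 7.1 aims it at patients starting Tresiba in routine Indian practice. Section 8.1.2 says no comparator is needed, and section 8.7 limits the analysis to descriptive statistics. The limitations in section 8.9 are the absence of a control arm, limited monitoring and incomplete data. How patients come to be chosen is not among them.

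**The concern.** Separating prescription from inclusion is proper in a non-interventional study, but it leaves a second choice open: which of the patients already prescribed Tresiba enter the study. With a quota of about 10 and no order of approach, a physician who has more eligible starters than places decides who fills them. Several features could influence that choice: a diary (8.4.1), visits over one year (8.3.1), no recall after a missed visit (8.4.1), and an exclusion that turns on the patient's willingness and ability to cooperate (8.2.3).

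With no control group, the AE incidence carries over to routine users only so far as the enrolled patients resemble them. More patients narrow the confidence interval but leave a selection bias unchanged. The order of approach is fixed at the site before any data exist, so a statistical analysis plan could not repair it later.

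**Working it through.** **The plan's own figures.** 100 sites × 10 patients = 1000, which agrees with the stated total. Section 8.5 starts from "A sample size of 1000 patients, assuming 20% dropouts", and section 8.2.1 gives "Planned number of patients to complete the study: 800"; 1000 × 0.8 = 800. The detection claim, "will provide a probability of 80% of detecting at least one event that occurs with an incidence of 2 in 1000 patients", reproduces: 1 − (1 − 0.002)^800 = 0.798. These figures are sound as binomial calculations. They take the enrolled patients to carry the same risk as the starters they stand for.

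**The texts side by side.** Section 8.1.1 gives the choice to the physician. Section 8.4.1 says what happens to a patient who has been assessed and found eligible. If a site sees more eligible starters than places and stops at about 10, section 8.4.1 cannot apply to all of them, and nothing says which ones it applies to. Sections 8.8.2 and 9.3 mention enrolment procedures only as papers for the ethics committee.

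**Size, by illustration only.** The protocol gives neither the number of starters per site nor any AE rate. Let f be the share of starters enrolled, r the AE risk in enrolled relative to non-enrolled starters, and p the incidence in all starters. Then p = f·p_E + (1 − f)·p_E/r, so the incidence in enrolled patients is p_E = p / [f + (1 − f)/r].

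With f = 1/3 and r = 0.8, taking the non-enrolled rate as 1: all starters (1/3)(0.8) + (2/3)(1.0) = 0.933, and 0.8/0.933 = 0.857, so the reported rate is 14% low.

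With the direction reversed, f = 1/3 and r = 1.25: 1/[0.333 + 0.667/1.25] = 1/0.867 = 1.154, so the reported rate is 15% high.

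The table assumes p = 20%. The half-width is 1.96·√[p_E(1 − p_E)/1000]. The last column replaces 0.002 by 0.002/[f + (1 − f)/r] in the detection formula with n = 800.

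| r | f | Reported incidence | Bias (points) | 95% half-width (points) | P(at least one event), true 2/1000 |
|---|---|---|---|---|---|
| 0.8 | 10% | 16.3% | −3.7 | 2.3 | 72.9% |
| 0.8 | 25% | 16.8% | −3.2 | 2.3 | 74.0% |
| 0.8 | 50% | 17.8% | −2.2 | 2.4 | 75.9% |
| 0.5 | 10% | 10.5% | −9.5 | 1.9 | 56.9% |
| 0.5 | 25% | 11.4% | −8.6 | 2.0 | 59.9% |
| 0.5 | 50% | 13.3% | −6.7 | 2.1 | 65.6% |
| 1.0 | any | 20.0% | 0 | 2.5 | 79.8% |
| any | 100% | 20.0% | 0 | 2.5 | 79.8% |

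Under these assumptions a moderate difference in risk gives a bias about as large as the sampling error or larger. With no difference in risk, or no surplus of starters, there is none.

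**The case against.** The strongest reply is that section 8.4.1 is mandatory: an eligible patient is enrolled, and the wording in 8.1.1 merely spreads 1000 patients over 100 sites. That narrows the gap without closing it, because 8.4.1 does not say who is approached once eligible starters outnumber places.

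The surplus itself is not shown. Data collection runs from January 2014 to January 2016 (section 5) with one year of follow-up, which leaves about 12 months to recruit. Ten patients per site is then under one a month (10/12 = 0.83). Enrolling one third of starters implies about 30 per site, a number the protocol does not give. This objection stands: some sites may have no choice to make.

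A reader might infer that physicians will pick healthier or more compliant patients and so push the incidence down. The documents do not support that. Sections 8.4.1 and 8.4.1's visit lists collect AEs by diary and by questioning at each contact, so good attenders may have more events recorded. The reasons for starting Tresiba listed for Visit 1 include hypoglycaemia and side effects of earlier therapy, and physicians might favour such patients. The net direction is open.

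It is also fair that the study has aims besides estimating an incidence: section 6 includes finding unexpected reactions, and section 8.5 is built on seeing at least one event. The 100 primary and secondary care sites, broad eligibility and baseline tables on the safety set (8.7.1) help a reader judge the patient mix. They do not show who was left out. Finally, enrolment papers sent to ethics committees are not at hand and could hold a sequence rule, so the statement that none exists is limited to this protocol.

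**Conclusion.** The point holds as an opportunity for selection bias that the protocol leaves open and does not acknowledge. Where a site has more eligible Tresiba starters than places, the enrolled patients may differ from routine starters, and the single-arm AE incidence may not describe routine users. It would go too far to say that the incidence does not describe them: neither the presence of selection nor its direction can be shown from the protocol. The 14% and the table rest wholly on assumed values of f, r and p, and the bias is zero where there is no surplus. Nor is the sentence in section 8.2.5 a defect; separating prescription from inclusion is what a study of this type needs. The change is still worth making, because consecutive invitation removes a source of bias in the primary result at almost no cost and cannot be supplied afterwards.

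**What to change.** - **Section 8.1.1:** replace physician selection with consecutive enrolment. Each site invites every eligible patient starting Tresiba, in the order in which they present, until about 10 have consented.
- **Reporting:** give, with the patient disposition, one aggregate count per site of eligible patients invited but not enrolled, with no individual data. Section 8.2.2 requires consent before any protocol-driven recording of data, so a log of the characteristics of people who did not consent, even de-identified, would sit badly with that rule.
- **Section 8.9:** add patient selection to the limitations.

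Treatment, visits and tests are unaffected. The cost is one sentence in 8.1.1, one line in 8.9 and slightly more site paperwork. Adherence to the order would go largely unverified, since section 8.8.1 provides for monitoring only case by case. If the sponsor already intends consecutive enrolment, the protocol need only say so.

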#### 8.1.2 Rationale for study design

The study is assessing the safety profile of Tresiba® used in patients under normal clinical practice conditions without any intervention, in India and without a comparator as it is not considered needed. The 1 year observation period is expected to be sufficient to capture untoward medical occurrences that are likely to be associated with long-term use of Tresiba®. Frequency and timing of visit are based on normal clinical practice for patients with diabetes mellitus requiring insulin therapy in India.

#### 8.1.3 Treatment of patients

Patients with diabetes mellitus requiring insulin therapy who qualify for starting treatment with Tresiba® based on the clinical judgment by their treating physician will be treated with Tresiba® according to routine clinical practice at the discretion of the treating physician. The assignment of the patient to Tresiba® is not decided in advance by the protocol but falls within current practice and the prescription of the medicine is clearly separated from the decision to include the patient in the study. Tresiba® will be prescribed by the physician under normal clinical practice conditions and will be obtained/ purchased from the chemist based on physician prescription. The physician will determine the starting dose, as well as later changes to dose, if any. Tresiba® should be used in accordance with the Indian package insert

#### **8.1.4 Rationale for treatment**

Diabetes patients will often require insulin in treatment continuum to control their blood glucose when the other available therapy options fail to keep to the recommended target appropriate to respective age group. The clinical practice in India is to add insulin, either basal or premixed depending on the requirement by the patient on existing therapy. The physician will decide as per patient requirement and add basal insulin therapy Tresiba® as per the Indian Package insert. Dosage and administration are based on the Indian package insert of Tresiba®. Further details about Tresiba® can be found in the Indian package insert.

#### **8.1.5 Study supplies**

##### **Study product:**

The following marketed products will be used in this PMS/PASS. They will not be provided by Novo Nordisk.

- Tresiba® FlexTouch® prefilled pen injector (100 U/mL)

##### **Packaging and labelling of study product(s):**

These must be as available in the market by prescription and purchase/supply as in routine practice and according to local regulations.

##### **Auxiliary supply:**

Not Applicable

### **8.2 Setting**

#### **8.2.1 Number of patients to be studied**

Planned number of patients to be included: 1000

Planned number of patients to complete the study: 800

Anticipated number of patients to be included in each country: India only-1000

#### **8.2.2 Inclusion criteria**

1. Informed consent obtained before any study-related activities (Study related activity are any procedure related to recording of data according to the protocol). The historical data including the data before informed consent obtained (e.g., HbA1c, FPG, severe hypoglycaemia before the start of Tresiba® therapy) can be used for baseline data.
2. Patients with insulin requiring diabetes mellitus and who is scheduled to start treatment with Tresiba® based on the clinical judgment of their treating physician.

### **8.2.3 Exclusion criteria**

1. Known or suspected allergy to Tresiba®, the active substance or any of the excipients
2. Previous participation in this study
3. Mental incapacity, unwillingness or language barriers precluding adequate understanding or cooperation.
4. Patients who are or have previously been on Tresiba® therapy.
5. Patients who are participating in other studies or clinical trials
6. Patients who are pregnant, breast feeding or have the intention of becoming pregnant within the following 12 months

[figure not shown]
### **8.2.4 Withdrawal criteria**

1. The patient may withdraw at will at any time.
2. The patient may be withdrawn from this PMS/PASS study at the discretion of the physician due to a safety concern.

